Per Protocol (PP) Population – The PP population includes all participants in the AUS ITT population who complete Virtual Visit 2 or have sufficient medical and medication history information and, when necessary, a verified LDL-C value collected prior to stopping the study in order to determine a final use outcome.

Safety Population – the Safety population includes all participants in the AUS ITT population who take at least one dose of IP as determined by returning fewer pills than dispensed, including those who do not return any bottles for pill counting. As such, any participants who return all pills delivered to them are excluded.

Participant and subject disposition will be summarized using the Pre-Screened Eligible and Registered and Pre-Screen Failure populations in the study database. In addition to disposition, subject’s reasons for failing the inclusion and exclusion criteria from the pre-screener will be summarized. Participant characteristics and demographics will be summarized on the SS population. The reasons for exclusion from the SS, AUS ITT and PP populations will be listed.

Analysis of the first co-primary endpoint (i.e., Overall Correct Initial TASS Outcome) will be conducted on the SS population as the primary analysis population; however, a second evaluation using the AUS ITT population and PP population will also be performed. Analysis of the second co-primary endpoint (i.e., Overall Correct Final Use Outcome) will be conducted on the PP population as the primary analysis population. Analysis of the third co-primary endpoint (i.e., PCFB in verified LDL-C to Visit 2) will be conducted on the AUS ITT population as the primary analysis population. Analyses on the secondary and exploratory endpoints will be conducted on the AUS ITT or PP populations as specified in [Sections 4.2.3](#) and [4.2.4](#).

All safety analyses will be conducted on the Safety population.

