Since participants are given a limited supply (i.e., 45 or 90 day) of rosuvastatin with each reorder, they are likely to have multiple reorder assessments over the duration of the trial. While this will occur, the critical reorder assessment will always be the last one taken by the participant since the corresponding TASS outcome represents their final use outcome. For the purposes of this study, a participant’s *final use assessment* will refer to the last reorder assessment they received during the study which includes the final use assessment taken at Virtual Visit 2. The TASS outcome resulting from the final use assessment will be utilized as the final use outcome for the Overall Correct Final Use Outcome co-primary endpoint.

The final use assessments will be determined based on the following criteria:

1. For participants who get an “OK to Use” outcome with each reorder, their final use assessment will be performed at the end of the 6-month use period during their Virtual Visit 2.
2. For participants who get a “Do Not Use” outcome as their last reorder assessment prior to the end of the 6-month use period, their Virtual Visit 2 will occur earlier. The last reorder assessment which resulted in the “Do Not Use” outcome will be used as their final use assessment.
 - a. Note that a “Do Not Use” outcome occurs whenever a participant meets Drug Facts Label (DFL) or LDL-C lowering criteria that would require the participant to stop treatment. This means that a participant who meets a *Stop Use* or *Do Not Use* criterion from the DFL will receive the same “Do Not Use” outcome and be evaluated as “Do Not Use” for the purpose of the second co-primary endpoint. For the purpose of evaluating the secondary endpoints, the reasons for the “Do Not Use” outcomes will be assessed in order to place them in the appropriate category for evaluation. In other words, participants who received a “Do Not Use” outcome due to a *Stop Use* criterion in the DFL will be assigned to the *Stop Use* category for evaluation.
3. For participants who get an “Ask a Doctor” outcome during the use period, they will be given until the end of the 6-month use period to speak to a doctor. Since subjects cannot reorder drug until they speak to the doctor, the risk of continuing them in the study is low. Importantly, allowing them to continue for the full 6-months provides the opportunity to assess whether they will contact a doctor at some point.

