instance where a participant has not reordered study drug, and thus does not have a reorder assessment, the final use outcome for the participant used in assessing the Overall Correct Final Use Outcome will be missing. These missing outcomes will not be imputed using the participant verbatim response as these participants were directed to discontinue from treatment by the CMOG, not at their own decision. The Overall Final Use Outcome from the standpoint of the second co-primary endpoint would be coded as “Incorrect”. Refer to [Section 3.2.6](#) for details on how these subjects will be handled for the Overall Correct Final Use Outcome.

Missing CMOG TASS Assessments

When there is a missing CMOG Final Use Outcome and an outcome cannot be determined using the TASS tool due to incomplete medical and medication history, the CMOG clinician will use the DFL and follow an algorithm based on the question flow of the TASS tool to make a determination. For details on the flow of the TASS tool at the reassessments, refer to 3.2.R in the initial investigational new drug (IND) submission sequence 0032. In order to determine a final use outcome for the CMOG at the final use assessment, the outcome will be assigned in a hierarchical order based on the information supplied in the medical and medication history. The hierarchical order of the outcomes to be assigned is as follows: “Do Not Use”, “Ask a Doctor” and “Ok to Use”. The CMOG outcome will be determined from their corresponding responses provided in Targeted Medical and Medication History Form at Virtual Visit 2.

- For a CMOG final use outcome to be determined as “Do Not Use” (or “Stop Use”), the CMOG must have provided an answer of “Yes” to any of the questions associated with a Do Not Use warning in the Targeted Medical and Medication History Form.
- For a CMOG final use outcome to be determined as “Ask a Doctor”, all answers to the questions associated with a Do Not Use warning must be answered as “No” before assessing the answers to the questions associated with an Ask a Doctor warning. In the event that there are incomplete answers to the Do Not Use associated questions, an “Ask a Doctor” outcome is not able to be determined and the CMOG final use outcome will be missing.

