- For a CMOG final use outcome to be determined as “Ok to Use”, all answers to the questions associated with Do Not Use and Ask a Doctor warnings must be answered as “No”. By default, an “Ok to Use” final use outcome can only be obtained when the CMOG clinician has answers to all the questions that are asked in the TASS tool. This includes having an LDL-C retest with an adequate response for participants who have continued in the study for 3 or more months. Thus, all “OK to Use” final use outcomes should be coming via a TASS assessment.

In those instances where a participant, CMOG or both TASS assessments are missing such that an Overall Final Use Outcome cannot be determined, the impact of the missing information will be assessed using the prespecified sensitivity analyses (see [Section 4.2.2](#)).

Missing CMOG initial TASS assessments should be rare or non-existent. In the event the CMOG is unable to perform a TASS assessment at Visit 1, the CMOG clinician will use the

DFL and follow an algorithm based on the question flow of the TASS tool to make a determination as described above. If the CMOG is unable to make a determination, the initial outcome will be missing.

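### The fallback rule for the clinician's final use outcome has no LDL-C route to Do Not Use, so a verified LDL-C non-response with an incomplete history is coded Missing or, rarely, Ask a Doctor in co-primary 2

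*SAP*

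**What the plan says.** SAP 3.2.3.3 (Missing CMOG TASS Assessments) covers the case where the tool gives no clinician outcome because the medical and medication history is incomplete. In that case "the CMOG clinician will use the DFL and follow an algorithm based on the question flow of the TASS tool to make a determination". On the data source it states: "The CMOG outcome will be determined from their corresponding responses provided in Targeted Medical and Medication History Form at Virtual Visit 2". The outcome is then assigned in the order Do Not Use, Ask a Doctor, OK to Use:

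- **Do Not Use** must rest on a 'Yes' to "any of the questions associated with a Do Not Use warning in the Targeted Medical and Medication History Form".
- **Ask a Doctor** needs every Do Not Use question answered 'No'. "In the event that there are incomplete answers to the Do Not Use associated questions", the outcome is Missing.
- **OK to Use** needs every answer: "This includes having an LDL-C retest with an adequate response for participants who have continued in the study for 3 or more months". The SAP adds that these outcomes should come through the TASS itself.

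Elsewhere LDL-C has a larger role. On Do Not Use, item 2a of SAP 3.2.3 states that this "outcome occurs whenever a participant meets Drug Facts Label (DFL) or LDL-C lowering criteria that would require the participant to stop treatment". The same section makes no change, an increase, or a second inadequate response a Do Not Use result. It also says that the clinician's final outcome draws on the history and the verified LDL-C together. The Do Not Use warnings listed in SAP 3.2.7 are events, conditions and medicines, with no LDL-C item. Protocol Section 8 (Virtual Visit 2) takes the verified LDL-C from the Diagnostics source, separately from the interview.

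**The concern.** LDL-C enters the fallback on one side only: a poor result can block OK to Use but cannot establish Do Not Use. A participant whose verified LDL-C has not fallen may therefore get no clinician outcome, although SAP 3.2.3 treats that result as decisive.

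The primary analysis of co-primary 2 keeps only participants with a non-missing outcome from both participant and clinician (SAP 4.2.2). Three things can go wrong:

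- A participant with OK to Use and a verified rise is an Incorrect Selection in SAP Figure 2. Coded Missing, this participant drops out of the denominator.
- A participant who received Do Not Use because of the rise is a Correct Rejection. That success is lost.
- If the clinician's code becomes Ask a Doctor, a participant Do Not Use is scored an Incorrect Rejection, and a participant Ask a Doctor is scored correct when it should not be.

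The first and last errors raise the observed rate; the others lower it.

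**Working it through.** **1. The plan's own figure.** SAP 1.3 states at least 90% power with n = 500, a true rate of 90%, and success if the exact 95% lower bound exceeds 85%. The Clopper-Pearson lower bound for x correct of n is the 0.025 quantile of Beta(x, n − x + 1). For n = 500 the smallest passing count is x = 441 (lower bound 85.04%; 440 gives 84.82%). P(X ≥ 441 | 500, 0.90) = 0.919 and P(X ≥ 441 | 500, 0.85) = 0.0235. The stated power reproduces.

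**2. The fallback bullets applied to a verified LDL-C non-response** (3 or more months in study):

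| Do Not Use questions | Ask a Doctor questions | Fallback result | SAP 3.2.3 result |
|---|---|---|---|
| a 'Yes' | any | Do Not Use | Do Not Use |
| incomplete, no 'Yes' | any | Missing | Do Not Use |
| all 'No' | a 'Yes' | Ask a Doctor | Do Not Use |
| all 'No' | incomplete, no 'Yes' | Missing | Do Not Use |
| all 'No' | all 'No' | none: OK to Use is barred | Do Not Use |

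Only the first row agrees, and there the outcome comes from an unrelated warning. The last row arises only if some other item needed by the tool is unanswered; otherwise the tool can be run with the verified LDL-C and returns Do Not Use. The Ask a Doctor row likewise needs another unanswered item, so it is a thin set.

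**3. Whether other provisions catch these cases.** The Missing LDL-C mitigation (SAP Appendix D) requires the LDL-C to be missing; here it is present and verified. Lost Opportunity requires the clinician to have found the drug OK to use. The best-case, worst-case and tipping-point analyses (SAP 4.1.3.2) include the Missing cases but treat a determinable result as unknown. They do not touch a case coded Ask a Doctor.

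**4. Effect on the lower bound.** The documents give no count, so the number k of affected participants is an assumption, shown from 1 to 20. Base case: 450/500 correct, lower bound 87.03%.

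- All k had OK to Use and enter as Incorrect, 450/(500 + k): k = 5 gives 86.06%, k = 10 gives 85.12%, k = 11 gives 84.93% and k = 15 gives 84.20%. Success is lost from k = 11. From 445/500 it is lost at k = 5 (445/505, 84.97%), and from 441/500 at k = 1 (441/501, 84.85%).
- All k had Do Not Use and enter as Correct, (450 + k)/(500 + k): k = 5 gives 87.16%, k = 10 gives 87.28% and k = 20 gives 87.52%.
- Five cases within the 500 move from clinician Ask a Doctor to Do Not Use and so become Correct: 455/500 gives 88.14%.

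Seen from the other side, 438/500 fails (84.39%). Leaving out three Incorrect cases still fails (438/497, 84.96%), and leaving out four passes (438/496, 85.15%).

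**The case against.** The strongest reply is that this is an incomplete bullet and not a decision to ignore LDL-C. The lead-in ties the algorithm to the TASS question flow and refers to an IND section. Neither that flow nor the history form is in the documents. Appendix A shows that the tool exits on LDL-C results, and SAP 3.2.3 gives the general rule of history plus verified LDL-C. The list in SAP 3.2.7 may also not match the form's questions exactly, since the bullet extends to Stop Use. All of this stands as a reason not to read intent into the gap. It does not remove the conflict: the bullet says 'must' and names only the form, so two clinicians could code identical cases differently.

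A reader might infer that the per-protocol definition lets an LDL-C alone settle the outcome. It does not: it asks for sufficient history information and, "when necessary, a verified LDL-C value collected prior to stopping the study in order to determine a final use outcome". Protocol 9.4.2.1 also makes the clinician evaluation missing when the participant will not give enough history. Some of the missingness is therefore a stated choice.

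A reader might also infer that the gap flatters the result. The documents do not support a fixed direction. A participant who enters a rise gets Do Not Use from the tool. Those with Do Not Use outcomes and those who discontinue get no study mandated LDL-C test. Discontinuers who refuse the final TASS can be coded only Do Not Use or Ask a Doctor (SAP 3.2.3.3). Lost Correct Rejections are thus at least as plausible as dropped Incorrect Selections.

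Finally, a conflict between the adequate-response condition and Table A2 scenario 1 may seem to follow, because a first inadequate response there gives OK to Use. It does not, since SAP 3.2.3.3 sends OK to Use outcomes through the TASS and scenario 1 is a TASS outcome.

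**Conclusion.** The point holds as an internal conflict in how a co-primary outcome is derived. As written, SAP 3.2.3.3 gives a verified LDL-C non-response no route of its own to Do Not Use, while SAP 3.2.3 makes it one. It bites only when the history is incomplete, the tool cannot be completed and no other Do Not Use question is 'Yes'. Then the code is Missing or, in few cases, Ask a Doctor.

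The number affected is not given and is probably small. At the planned 90% rate, about 11 one-directional cases would be needed to change the conclusion; close to the 85% bound, one to five would do. These figures rest on assumed counts and on every case falling the same way, so they show sensitivity and do not predict bias. It would go too far to say that the fallback never returns Do Not Use for a non-responder: another 'Yes' still does so, and with a complete history the tool does. The change should be made before database lock because the derivation is co-primary and the cost is very low.

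**What to change.** Amend the first bullet of the fallback in SAP 3.2.3.3 to agree with SAP 3.2.3. For coding the CMOG final use outcome, the most recent verified LDL-C on the Visit 2 Diagnostic Report gives Do Not Use if it meets the SAP's existing Do Not Use criterion, and this is checked before the Ask a Doctor step. Two limits are needed:

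- Apply it directly to a verified result of no change or an increase, as Appendix A scenarios 14 and 15 already do.
- Apply it to inadequate responses only where Appendix A's requirement of two verified values is met (scenario 10). Otherwise keep Missing, as in scenarios 1b, 5, 6 and 8.

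List the participants whose clinician outcome came from the fallback and who had a verified LDL-C non-response, with the participant outcome, so that the effect on co-primary 2 can be seen in both directions.

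The cost is one or two sentences and one listing. The verified LDL-C is already collected; no procedure, visit or clinical rule changes.

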3.2.4 Incorrect TASS Entries

After a participant enters information into the Web App during the initial TASS assessment or final use assessment, the CMOG clinician will conduct a targeted medical and medication history evaluation. The clinicians in the CMOG are blinded to the entries made by the study participant in the Web App. Once this interview is complete, the Central Assessor will compare the self-selection outcome from the participant in Web App to the TASS entries from the CMOG. Information obtained by the Central Assessor is not shared with the CMOG clinician. These roles perform independent functions for purposes of this study.

- For those participants proceeding into the actual use portion of the study: follow-up probes will be asked for any discrepancies between TASS entries that are only asked at the initial self-selection assessment as well as any Web App use errors.
- For those participants who do not meet the criteria for proceeding into the actual use portion of the study: follow-up probes will be asked of a participant for any discrepancies between TASS entries as well as Web App use errors.

The follow-up questions are not used for adjustment of the self-selection results; this information is used to determine the root cause of any discrepancies between the medical and medication history and Web App entries. Verbatim responses to these follow-up probes will be categorized based on the reasons for the discrepancies for each TASS question.

3.2.5 Cholesterol Retesting

During the use period of the study, participants will be told through the Web App and transactional emails to retest their LDL-C within 3 months. During the reorder assessments, participants are asked to input their number to ensure they are getting an adequate therapeutic response. These LDL-C retest values will be verified at the participant's Virtual Visit 2.

Participants who should retest are those who were eligible for continuous treatment and who completed Virtual Visit 2.

3.2.6 Stop Use Warnings

Prior to every drug reorder, participants are required to enter the Web App and take an abbreviated medical reorder assessment. If a participant identifies a "Stop Use" warning, they are instructed by the Web App to both stop use and contact a doctor and will no longer be able to order drug. Stopping use can be ensured through the Web App by preventing participants from reordering medication; however, the participant must take the initiative to contact a doctor.

While the information used to assess stopping use can come from either the Web App or the Targeted Medical and Medication History Form at Virtual Visit 2, the information used to assess contacting a doctor will come from the Targeted Medical and Medication History Form completed by the clinician at Virtual Visit 2.

There are two “Stop Use” warnings for non-prescription rosuvastatin: (1) severe and unexplained muscle pain, tenderness, or weakness and (2) symptoms of liver problems (upper belly pain, dark urine, yellowing of skin or whites of eyes).

While some individuals may identify these symptoms and have treatment stopped through the use of the Web App, there is a reasonable probability that people with these symptoms will simply stop therapy and decide not to use the Web App because they do not want to reorder medication. Meeting the second co-primary endpoint and the secondary endpoint with regard to “Stop Use” warnings requires the participant to identify the “Stop Use” warning on their own. If during the planned 60- and 120-day touchpoint, following review of the eDiary, or through an unplanned contact from the participant, a “Stop Use” criterion is identified, the participants will be managed as follows:

- If during the interview with the clinician, the participant volunteers that they had a “Stop Use Warning”, they will be scheduled for Virtual Visit 2. Participants who self-identify a “Stop Use” criterion will complete all Virtual Visit 2 procedures including a TASS assessment.
- If, on the other hand, the CMOG becomes aware of a “Stop Use” criterion during the telephone call that the participant did not identify, all Visit 2 procedures except a participant TASS and SMT for LDL-C will be performed. The reason for not repeating the TASS is that the participant did not self-identify the “Stop Use” criterion. Instead, the CMOG identified the criterion and discussed with the participant, which could bias the participant’s behavior when completing the TASS. For example, a participant who did not realize they should have stopped drug because of severe muscle symptoms, may answer “yes” to this question in the TASS and be categorized as a correct selector when, in reality, they may have answered “no” to this question if they had not spoken to a CMOG clinician prior to completing the TASS. For those participants who have completed a reorder assessment, the most recent TASS reorder assessment will be used as the final TASS assessment, and the corresponding outcome will be used as the final use outcome for the participant. For those participants who have not completed a reorder assessment, the final use outcome for the participant will be considered missing. As mentioned in [Section 3.2.3.3](#), these missing outcomes will not be imputed using the participant verbatim response as these participants were directed to discontinue from treatment by the CMOG, not at their own decision. Because the study staff had to inform the participant that they met a “Stop Use” criterion, they will be considered a failure (i.e., incorrect) when evaluating the second co-primary endpoint related to “use.”
- Participants who the CMOG clinician identifies as having experienced “Stop Use” criteria are considered “Discontinued from Study Intervention” and not a withdrawal (refer to [Section 3.1](#)). In general, the only events recorded in an eDiary or communicated to the study

staff during a phone check that would result in study medical personnel instructing the participant to stop taking rosuvastatin are “Stop Use” criteria. If such a situation occurs, the participant will be classified as a discontinuation from study intervention due to “Adverse Event” or “Pregnancy” and scheduled for a Virtual Visit 2.

See [Appendix B](#) for additional details on how the participant’s final use outcome would be assessed based on these different scenarios.

